4.2. General Statistical Methods and Data Handling

4.2.1. **General Methods**

All output will be incorporated into Microsoft Excel or Word files, sorted, and labeled according to the International Council on Harmonisation (ICH) recommendations, and formatted to the appropriate page size(s).

Tabulations will be produced for appropriate demographic, baseline, efficacy, pharmacokinetic and safety parameters. For categorical variables, summary tabulations of the number of missing, and number and percentage of each category of the parameter will be presented by treatment groups and visits (as applicable). For continuous variables, the n, mean, standard deviation, median, minimum, and maximum values will be presented.

The baseline visit will be defined as the last non-missing measure prior to initiation of investigational treatment. Differences between treatment groups will be calculated as OTX-CSI minus HV, and change from baseline will be calculated as follow-up visit minus baseline visit values.

All statistical testing will be done at the two-sided alpha level of 0.05.

Sponsor:	Ocular Therape	Ocular Therapeutix, Inc.			
Protocol:	CLN-Protocol-0054				
Document Version No.:	V1.0	V1.0 Document Date: 01-OCT-2021			

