4.7.3. Secondary Analyses

1. To analyze the efficacy endpoint of percent of eyes with ≥10 mm Increase in Schirmer Test from Baseline at Visit 7 (Week 12) and other Post-Baseline Visits, the logistic regression or Fisher's exact test will be used as described below:

The two groups of Schirmer test (≥10 mm vs <10 mm) will be compared between treatment groups as CSI Formulation 1 to HV Formulation 2B, CSI Formulation 2A to HV Formulation 2B, CSI Formulation 1 to HV Formulation 3, CSI Formulation 2A to HV Formulation 3, will be reported. This model will also be used to compare overall OTX-CSI (combined Formulation 1 and Formulation 2A) to each HV Formulation (2B and 3) using the logistic regression.

The above analyses will be performed on the change from baseline in Schirmer test (\geq 10 mm vs <10 mm) derived based on the imputed Schirmer data using FCS MI (details in section 4.2.9.1) at visit 7 on the mITT and PP populations using the logistic regression and Odds Ratio (OR), 95% confidence interval for OR, and P-value for OR will be reported. In addition, sensitivity analyses will be done using LOCF and observed data and the two groups of Schirmer test (\geq 10 mm vs <10 mm) will be compared between treatment groups using the Fisher's exact test on this endpoint. These analyses will also be performed on all post-baseline visits.

2. To analyze the efficacy endpoints of Eye Dryness Severity and Eye Dryness Frequency, statistical modeling similar to the primary efficacy endpoint analysis (4.7.1) will be performed for each post-baseline visit (Visit 3, Visit 4, Visit 5, Visit 6, Visit 7, and Visit 8)

Sponsor:	Ocular Therapeutix, Inc.		
Protocol:	CLN-Protocol-0054		
Document Version No.:	V1.0 Document Date: 01-OCT-2021		

using the MCMC MI imputed data on the mITT and PP populations. In addition, sensitivity analyses done for the primary efficacy endpoint will also be performed on this endpoint.

3. To analyze the efficacy endpoints of total Corneal Fluorescein Staining (tCFS) and its sub-region, statistical modeling similar to the primary efficacy endpoint analysis (4.7.1) will be performed for each post-baseline visit (Visit 3, Visit 4, Visit 5, Visit 6, Visit 7, and Visit 8) using the MCMC MI imputed data on the mITT and PP populations. In addition, sensitivity analyses done for the primary efficacy endpoint will also be performed on this endpoint.

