5. CHANGES TO PLANNED ANALYSES

The language in the SAP will supersede the language in the protocol should there be a discrepancy.

The primary analysis will be repeated for all visits using observed data (without imputation) for both mITT and PP populations. These results will be provided in sensitivity analyses section.

The difference between two OTX-CSI hydrogel formulations as well as the difference between two HV formulations will not be studied. HV formulations will not be combined.

Wilcoxon rank sum test will be used only to analyze LOCF and observed data.

For Eye Dryness Severity and Eye Dryness Frequency, as well total Corneal Fluorescein Staining (tCFS) and its sub-region the main analysis will be based on MCMC MI and sensitivity analyses will be done using LOCF, observed data, and FCS.

For the first secondary efficacy endpoint analysis, for the main analysis, the two groups of change from baseline in Schirmer test (\geq 10 mm vs <10 mm) at visit 7 will be compared between treatment groups using the logistic regression and for the sensitivity analyses, the groups will be compared using LOCF and observed data by Fisher's exact test; Clopper-Pearson method will be used to calculate 95% confidence interval of the proportion of subject with change from baseline in Schirmer Test \geq 10 mm; to calculate 95% confidence interval of the proportion difference, the Chan and Zhang (1999) method will be used.

These analyses will also be performed on all post-baseline visits.

Sponsor:	Ocular Therapeutix, Inc.		
Protocol:	CLN-Protocol-0054		
Document Version No.:	V1.0 Document Date: 01-OCT		01-OCT-2021

6. **REFERENCES**

American Academy of Ophthalmology Cornea/External Disease Panel. Preferred Practice Pattern[®] Guidelines. Dry Eye Syndrome. San Francisco, CA: American Academy of Ophthalmology; 2018. Available at www.aao.org/ppp. Accessed September 23, 2019.

- Disease in the United States Among Adults Aged 18 Years and Older. Am J Ophthalmol. Oct;182:90-98.
- Perry HD. Dry eye disease: Pathophysiology, classification, and diagnosis. Am J Manag Care. 2008;14:S79-S87.
- Schultz C. Safety and efficacy of cyclosporine in the treatment of chronic dry eye. Ophthalmol Eye Dis. 2014;6:37-42.

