7.3. SAS Codes

7.3.1. variables used in SAS codes:

TRPG1N	Treatment groups with 4 groups
TRPG1N_FG1	Dummy variables based on TRPG1N
TRPG1N_FG2	
TRPG1N_FG3	
AVAL2	Value at visit 2
AVAL4	Value at visit 3
AVAL5	Value at visit 4
AVAL6	Value at visit 5
AVAL7	Value at visit 6
AVAL8	Value at visit 7
СНБ	Change from baseline
CRIT4	Categorical Schirmer test (>=10 mm vs <10 mm) at visit 3
CRIT5	Categorical Schirmer test at visit 4
CRIT6	Categorical Schirmer test at visit 5
CRIT7	Categorical Schirmer test at visit 6
CRIT8	Categorical Schirmer test at visit 7
CRIT9	Categorical Schirmer test at visit 8
SEFN	Study eye flag

Sponsor:	Ocular Therapeutix, Inc.		
Protocol:	CLN-Protocol-0054		
Document Version No.:	V1.0	Document Date:	01-OCT-2021

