7.3.4. SAS codes to run t-test on MI data

```
ods output statistics=ttest1;

proc ttest data=pr2;

by AVISITN IMPUT;

where TRPG1N in (1 3);

class TRPG1N ;

var CHG;
```

run;

Sponsor:	Ocular Therapeutix, Inc.			
Protocol:	CLN-Protocol-0054			
Document Version No.:	V1.0	V1.0 Document Date: 01-OCT-2021		

data ttest2;

set ttest1; if class="Diff (1-2)" and method ne "Pooled" then delete;

run;

ods output parameterestimates=pdiff_ttest; proc mianalyze data=ttest2; modeleffects mean; stderr stderr; by AVISITN CLASS;

run;

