7.3.5. SAS codes to run ANCOVA (using PROC MIXED) on MI data

ods output LSMESTIMATEs=LSMESTIMATEs; proc mixed data= pr2; by AVISITN IMPUT; CLASS TRPG1N (ref=last); MODEL CHG=TRPG1N base; Ismeans TRPG1N/ cl pdiff; LSMESTIMATE TRPG1N "1G1" **1000**, "2G2" 0 1 0 0, /* WF1 and WF2 are the sample size weighted coefficient for group 1 and 2 respectively*/ "3G(1/2)" &WF1. &WF2A. 00, "4G3" **0010**, "5G4" 0001, "6G1 vs G3" 10-10, "7G2 vs G3" **01-10**, "8G1 vs G4" **100-1**, "91G2 vs G4" 0 1 0 -1, "92G(1/2) vs G3" &WF1. &WF2A. -10, "93G(1/2) vs G4" &WF1. &WF2A. 0-1 / cl;

run;

proc sort data=LSMESTIMATEs; by AVISITN LABEL;

run;

Sponsor:	Ocular Therapeutix, Inc.			
Protocol:	CLN-Protocol-0054			
Document Version No.:	V1.0	Document Date:	01-OCT-2021	

ods output ParameterEstimates=outIsmean; PROC MIANALYZE DATA=LSMESTIMATEs; modeleffects estimate; stderr stderr; by AVISITN LABEL; RUN;

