7.3.6. SAS codes to generate and pool proportions using MI data

```
proc surveyfreq data= pr1fcsy;
            by avisitn imput;
            tables TRPG1*CRIT8 / row ;
            ods output CrossTabs=mi_perc_out;
```

run;

```
proc mianalyze data=mi_perc_out;
    by TRPG1 CRIT8;
    modeleffects RowPercent;
    stderr RowStdErr;
    ods output ParameterEstimates=pooled_percent;
run; quit;
```

7.3.7. SAS codes to generate and pool the Odds Ratio (OR) using MI data

```
ods output ParameterEstimates =OR_out;

proc surveylogistic data= pr1fcsy;

by avisitn imput;

class TRPG1 / param = ref;

model CRIT8 (desc) =TRPG1;

where TRPG1N in (1 3);

run;

proc mianalyze data=OR_out;
```

```
modeleffects Estimate ;
stderr StdErr;
ods output ParameterEstimates=pooled_OR;
```

run; quit;

Sponsor:	Ocular Therapeutix, Inc.			
Protocol:	CLN-Protocol-0054			
Document Version No.:	V1.0	Document Date:	01-OCT-2021	

7.3.8. SAS codes to output 95% CI for proportions using Clopper-Pearson method and 95% CI for the proportion difference using Chan and Zhang (1999) method using observed and LOCF data

ods output RiskDiffCol1=RiskDiffCol1 FishersExact=FishersExact;
proc freq data=adoe;

table TRPG1N* CRIT8 / fisher;

exact riskdiff(method=score);

run;

7.3.9. SAS codes to designate study eye randomly in a case both eyes have the same total corneal fluorescein staining score

- 1- Create a SAS dataset RND1 with 1000 observations,
- 2- Create a variable named FOCID. The first 500 observation with value of "OD" (Right Eye) the last
- 500 observation with value of "OS" (Left Eye)
- 3- Generate a random number using RANUNI (Uniform distribution)
- 4- Sort this dataset by random variable ****;

data rnd1;

```
do i=1 to 500;
FOCID="OD";
rand=ranuni(54603);
output;
end;
do i=501 to 1000;
FOCID="OS";
rand=ranuni(54603);
output;
end;
run;
proc sort data=rnd1(drop=i); by rand; run;
data rnd1; set rnd1; VSORT= n ; run;
proc sort data=rnd1; by VSORT; run;
****
5- Sort the subject by using 2 variables
```

```
a- date of randomization for randomized subjects / date of informed consent for open label subjects
```

- b- random number
- c- subject number

Sponsor:	Ocular Therapeutix, Inc.			
Protocol:	CLN-Protocol-0054			
Document Version No.:	V1.0	Document Date:	01-OCT-2021	

6- Then merge this dataset with RND1 and then selected FOCID will be their study eye.****; proc sort data=idsd.suppdm out=dm1(keep=USUBJID QVAL);

where QNAM="RANDNUMB";

by USUBJID;

run;

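### As printed in SAP 7.3.7, the odds-ratio pooling step for the 10 mm Schirmer responder endpoint averages the intercept with the treatment log odds ratio

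*SAP*

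**What the plan says.** SAP 4.7.3, item 1, sets the main analysis of the responder endpoint (increase of at least 10 mm in Schirmer from baseline) on data imputed by fully conditional specification, "using the logistic regression and Odds Ratio (OR), 95% confidence interval for OR, and P-value for OR will be reported". SAP 5 repeats that the two responder categories "at visit 7 will be compared between treatment groups using the logistic regression". SAP 4.2.9.1 fixes the number of imputations at 25.

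SAP 7.3.7 gives the code. It fits "model CRIT8 (desc) =TRPG1" with reference coding, by visit and imputation, restricted to treatment groups 1 and 3, and saves the whole parameter-estimates table as OR_out. SAP 7.3.1 defines CRIT8 as "Categorical Schirmer test at visit 7". The next step is "proc mianalyze data=OR_out", which names only the estimate column, the standard-error column and an output dataset. Between fit and pooling there is no BY, WHERE or data step.

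The SAP's other three pooling steps each carry a BY that separates distinct quantities. The t-test code (7.3.4) has "modeleffects mean; stderr stderr; by AVISITN CLASS". The ANCOVA code (7.3.5) first runs "proc sort data=LSMESTIMATEs; by AVISITN LABEL" and then pools by the same two variables. The proportion code (7.3.6) pools by treatment and response category.

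**The concern.** PROC MIANALYZE treats every row it receives within a BY group as one imputation's estimate of the same parameter. A two-arm logistic model fitted without NOINT yields an intercept row and a treatment row. With nothing to separate them, the procedure averages two different parameters and counts the gap between them as between-imputation variance. The estimate, standard error, confidence interval and p-value would then all be wrong.

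At stake is the main analysis of the first-listed secondary endpoint, to be judged under the general rule that "All statistical testing will be done at the two-sided alpha level of 0.05". SAP 5 says the SAP overrides the protocol where they differ, so the chi-squared test in protocol 11.7 is not a fallback. The output would not obviously look broken either: a modest negative log estimate with a wide interval resembles an ordinary null result.

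**Working it through.** The documents give no odds ratio or power figure for this endpoint, so there is no stated number to reproduce. The check traces the code and applies Rubin's rules.

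**Inputs from the documents.** Imputations m = 25 (SAP 4.2.9.1). Planned arms 40, 40, 40 and 20 (SAP 2.1). Intercept plus one treatment term, reference coding (SAP 7.3.7).

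**Assumed.** The responder rates. Large-sample logit variances with all subjects contributing. No variation between imputations except in the simulated checks at the end.

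**Step 1: what is pooled.** Two rows per fit gives 25 x 2 = 50 rows for one visit. If OR_out held all six visits (Visits 3 to 8) it would be 300, with visits mixed as well. The restriction to groups 1 and 3 selects subjects before the fit and leaves the intercept row in place.

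**Step 2: the pooled estimate.** With reference coding,

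- intercept a = logit(p_ref)
- slope b = logit(p_other) - logit(p_ref)
- pooled value = (a + b)/2 = logit(p_other)/2

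The reference rate drops out whatever the data. For any non-reference rate below 50% the pooled value is negative.

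**Step 3: the pooled variance.** Total = U + (1 + 1/50) x B, where U is the mean within-row variance and B the sample variance of the 50 estimates. The variances are var(a) = 1/[n_ref p_ref (1 - p_ref)] and var(b) = var(a) + 1/[n_other p_other (1 - p_other)].

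Worked case, 40 v 40, 20% (non-reference) v 10% (reference):

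- a = -2.197, var(a) = 1/(40 x 0.10 x 0.90) = 0.2778
- b = 0.811, var(b) = 0.2778 + 1/(40 x 0.20 x 0.80) = 0.4340
- pooled value = (-2.197 + 0.811)/2 = -0.693
- U = (0.2778 + 0.4340)/2 = 0.3559
- B = (50/49) x [(0.811 + 2.197)/2]^2 = 2.308
- total = 0.3559 + 1.02 x 2.308 = 2.710, so SE = 1.646, df = 65, p = 0.675

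The correct result is b alone: 0.811 with SE 0.659, OR 2.25, p = 0.22.

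**Step 4: other assumed rates.** Values are on the log scale the code returns.

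| Arms (other v ref) | Rates (other v ref) | Correct log OR (OR, p) | As printed (SE, p) |
|---|---|---|---|
| 40 v 40 | 20% v 10% | 0.811 (2.25, 0.22) | -0.693 (1.65, 0.68) |
| 40 v 40 | 30% v 5% | 2.097 (8.1, 0.009) | -0.424 (2.68, 0.87) |
| 40 v 40 | 20% v 20% | 0 (1.00, 1.00) | -0.693 (0.86, 0.42) |
| 40 v 20 | 40% v 10% | 1.792 (6.0, 0.027) | -0.203 (2.18, 0.93) |

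The last row assumes the same code is reused for a Formulation 3 comparison, with that arm as reference.

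**Step 5: with some responses imputed.** Two simulated runs, 40 v 40, about 10% of responses imputed:

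- 30% v 10%: treatment rows only, OR 3.76 (95% CI 1.08 to 13.12), p = 0.038. As printed and then exponentiated, 0.67 (0.02 to 27.38), p = 0.83.
- 30% v 5%: treatment rows only, log OR 2.031, p = 0.014. As printed, -0.390, p = 0.88.

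**Step 6: scale.** The printed code never exponentiates, so even a correct pool would return a log odds ratio, not the odds ratio promised in 4.7.3.

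**The case against.** The strongest objection is that the missing line may be an artefact of the published text. The code listing breaks immediately after the MIANALYZE call, which is where 7.3.6 has its BY line, and the appendix shows other extraction damage. The code is also plainly an excerpt. The step that turns the wide imputed data into one record per visit is not printed, dataset pr2 is never created, and sorts needed by the BY statements in 7.3.4 and 7.3.6 are absent. A row filter could be among the omitted steps. The prose in 4.2.9.1 and 4.7.3 is right, and a programmer working from it would pool the treatment log odds ratio. Finally, the pooled percentages from 7.3.6 and the Fisher analyses would conflict with a wrong odds ratio, and this Phase 1/2 study has no testing hierarchy or powering.

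Some of this stands. The fault is established only for the code as printed; the source file and production program have not been seen. The primary analysis is unaffected, and being listed first gives the endpoint no inferential priority. But no loss is shown, nothing elsewhere in the SAP supplies the row selection, and this is the only odds-ratio pooling code given. Where 7.3.4 needs a filter before pooling, it prints one. A conflict with the other tables might expose the error, but the plan should not rely on that.

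**Conclusion.** The concern holds for the code as printed. SAP 7.3.7 pools the intercept with the treatment effect and returns logit(p_other)/2, which does not depend on the reference arm. That result is algebra and needs no assumption about rates. The sizes do rest on assumed rates: at 30% v 5% with 40 per arm, a log odds ratio of 2.097 (p = 0.009) becomes -0.424 (p = 0.87), and with equal arms at 20% a true value of 0 becomes -0.693.

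Which arm is the reference depends on how the treatment variable is coded, which the SAP does not show, but the fault is the same either way. It affects the main analysis of the Schirmer responder endpoint and should be fixed. The primary Schirmer analysis and the Fisher analyses on LOCF and observed data do not use this step.

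**What to change.** 1. Check the SAP source file for a line lost after the MIANALYZE call in 7.3.7.
2. If none was lost, keep only the TRPG1 row of OR_out, sort by AVISITN, Variable and ClassVal0, and run PROC MIANALYZE with that BY list.
3. Exponentiate the pooled log odds ratio and its confidence limits before reporting.
4. For consistency, in 7.3.6 sort and pool by AVISITN, TRPG1 and CRIT8 if the input holds more than one visit.

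The cost is a few lines of SAS in the SAP appendix and a check that the production program matches. No protocol amendment and no new data are needed.
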